6.2.5 Missing data examples

Several examples are provided to illustrate how missing data will be handled according to the rules defined above. Importantly "missing data" under the primary estimand does not necessarily mean that data were not observed but rather actually missing data and observed data that is considered missing due to treatment discontinuation.

For each year (1st and 2nd season), calculating average TCS, DSS, DMS, and RQLQ is a simple average of the diaries' observed records (no imputation of daily data) for some specific period.

Figure 2: TCS trajectory.

The Figure 2 shows three imaginary subjects between the 20th of June, 2022 and the 1st of August, 2022, as an example of daily records of TCS. The hypotetical grass pollen season is from 20th of June to 1st of August, 2022. The three subjects have identical TCS trajectories but discontinue treatment at three different time points. Also, we consider the case for the PGPS (the case for the EGPS and the year 2023 are dealt with similarly).

Statistical analysis plan	Date:	27-Oct-2023	
Trial ID: SU-G-01	Version:	1.0	
EudraCT No.: 2020-000455-12	Status:	Final	
CONFIDENTIAL	Page:	27 of 47	

For these subjects, the 2022-PGPS lies between 24th of June and 7th of July, 2022.

- Subject (#1) discontinues IMP on 22nd.of June. Thus, the entire PGPS lies after IMP discontinuation; therefore, this subject has no observations. Consequently, all records pertaining to the PGPS in 2022 and 2023 must be imputed. The observed data until 22nd of June will be used for the estimation of average endpoints for EGPS for 2022.
- Subject (#2) discontinues IMP on 1st of July. This subject has observations between 24th June and 1st of July from the PGPS, and only these observations will be used as the basis for the subject's 2022 PGPS record. This subject is thus fully observed in 2022's EGPS and PGPS. Consequently, only imputations for 2023 will be performed.
- Subject (#3) discontinues IMP after the end of the PGPS 2022. All the subject's records from the PGPS will be used to calculate the average TCS, and consequently, only imputations for 2023 will be performed.

Consider one more subject, which is not illustrated in Figure 2:

• Subject (#4) discontinued IMP before 20th of June, 2022. Though this subject might have some recordings before the actual start EGPS 2022, but all the average endpoints will have to be imputed for both years.

There are several observations to be aware about from the example above:

- The pattern of missingness (and consequently the pattern of imputation) may differ within the same subject for EGPS and PGPS. This pattern is (for each endpoint/pollen season) either:
 - Completely missing (both years 2022 and 2023 are missing)
 - Observed in 2022 but missing in 2023 (monotone missing pattern)
 - Missing in 2022 and observed in 2023 (this can happen if diary data is, in fact, missing during, the relatively short PGPS (2 weeks) in 2022 but the subject otherwise completed the trial and treatment) (not monotone missing pattern)
- "Completer" is a subject that is observed during both years.
- The number of observations upon which a subject's observed (EGPS and PGPS) average data depend considerably among subjects.

6.2.6 Exploratory endpoint analysis

6.2.7 Supportive analyses

6.2.7.1 Tipping point analysis under the primary and secondary estimand The objective of tipping point analysis is to investigate the feasibility of alternative assumptions regarding missing data, leading to a change in conclusions. In other words, it aims to determine the threshold at which the evidence of a treatment effect no longer remains.

Statistical analysis plan	Date:	27-Oct-2023	
Trial ID: SU-G-01	Version:	1.0	
EudraCT No.: 2020-000455-12	Status:	Final	
CONFIDENTIAL	Page:	28 of 47	

The tipping point analysis will be performed as follows: a penalty (a number) is added to all imputed values in the active treatment group, and the analysis is repeated. The considered penalty step for TCS will be 0.5 and for RQLQ will be 0.05. The penalty is gradually increased until the point, the tipping point, where the null hypothesis is no longer rejected. If the value of the tipping-point is considered a clinical plausible this analysis does not support rejecting primary hypothesis.

The tipping point analysis will be performed for primary and first key secondary endpoints using trial product estimand main approach.

6.3 Supplementary analyses

6.3.1.1 Asthma subgroup analysis

The subgroup analysis will test if the effect of treatment differs between subjects with and without ongoing asthma at screening. The analysis will be performed on imputed data using primary and secondary estimand, main analysis approaches. To be specific, data will be analysed using a Mixed Model of Repeated Measurements (MMRM) with treatment, year; treatment and year interaction, and ongoing asthma status as fixed effects and country and year interaction as random class effect and allowing unequal R-matrices among the two treatment arms.

Treatment contrasts corresponding to each level of ongoing asthma status will be output along with multivariate tests of year-specific subgroup effects: that is, for each year, the two treatment contrasts are statistically significant from one another.

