6.3.1.3 Symptoms-score tertiles analysis

Howarth *et al.* (2012) examined effects of allergen immunotherapy where study sites were grouped by the level of allergic rhinoconjunctivitis symptoms (low, medium, high) among placebo-treated subjects. The hypothesis was that sites where the symptoms scores were the highest under placebo, the seasonal disease activity was the highest and, presumably, therefore an effect of the allergen immunotherapy could potentially be greater here than at sites where the symptoms scores under placebo were lower.

To address this, trial sites will be grouped into tertiles according to the trial sites' placebo mean TCS in the PGPS based purely on observed TCS values (i.e. no imputation) for each of the two years (2022 and 2023), respectively. TCS and RQLQ will be analysed for the PGPS using the

Statistical analysis plan	Date:	27-Oct-2023	
Trial ID: SU-G-01	Version:	1.0	
EudraCT No.: 2020-000455-12	Status:	Final	
CONFIDENTIAL	Page:	29 of 47	

ALK

DPS1/on-treatment observation period data. The model(s) will be ANCOVAs run for each year separately. The model will include treatment, seasonal-disease-activity-subgroup and asthma strata as fixed effects and allowing unequal residual variances among the two treatment arms.

Treatment contrasts corresponding to each level of trial-site-subgroup will be output along with (multivariate) tests of (year-specific) subgroup effects: that is, for each year, whether the three treatment contrasts (corresponding to the three tertiles subgroups) are statistically significant from one another.

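### The asthma and tertile subgroup models in SAP 6.3.1.1 and 6.3.1.3 contain no treatment-by-subgroup term, so the planned tests between subgroup contrasts cannot be computed; the tertile analysis also needs a different grouping variable before any test is valid.

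*SAP*

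**What the plan says.** SAP 6.3.1.1 gives its aim as: "The subgroup analysis will test if the effect of treatment differs between subjects with and without ongoing asthma at screening". The model it then specifies has "treatment, year; treatment and year interaction, and ongoing asthma status as fixed effects and country and year interaction as random class effect", and it allows the R-matrices to differ between the arms. This is the effect list of the main MMRM in SAP 6.2. The promised output is: "Treatment contrasts corresponding to each level of ongoing asthma status will be output along with multivariate tests of year-specific subgroup effects". The text explains that the two contrasts are to be compared within each year.

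SAP 6.3.1.3 groups sites into thirds by their observed placebo mean TCS in the peak season, separately for 2022 and 2023. TCS and RQLQ are then analysed with one ANCOVA per year: "The model will include treatment, seasonal-disease-activity-subgroup and asthma strata as fixed effects". The planned test asks "whether the three treatment contrasts (corresponding to the three tertiles subgroups) are statistically significant from one another".

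Neither section names an interaction between treatment and the subgroup. The model description in SAP 9.5.2 does not add one. The visible part of SAP Appendix A is only a heading, so nothing can be inferred from it either way.

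**The concern.** A test of effect modification needs a parameter that lets the treatment effect vary with the modifier. These two models have none, although the outputs asked of them presuppose one. The programmer must then either report that the test does not exist or choose an unwritten model. That choice is not trivial. With treatment x asthma alone, the asthma difference is forced to be the same in both years, whereas SAP 6.3.1.1 asks for year-specific tests.

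Asthma is not an incidental subgroup here. Protocol 1.4 reports that the earlier efficacy trial of a related 3-grass product was not significant overall, had more asthmatic subjects in the active arm, and was significant post hoc in subjects without asthma. Randomisation in the present trial is stratified on asthma. Readers will look for this analysis.

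**Working it through.** The plan states no figure for the subgroup tests, so the check is mainly algebraic.

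**Asthma model as written.** Let T, Y and A be 0/1 indicators for active, 2nd year and asthma. The fixed part is

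b0 + b1·T + b2·Y + b3·A + b4·T·Y.

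- 1st-year contrast, active minus placebo: b1 if A = 0 and b1 if A = 1.
- 2nd-year contrast: b1 + b4 if A = 0 and b1 + b4 if A = 1.
- The difference between asthma levels has coefficient vector (0, 0, 0, 0, 0) in each year: rank 0, no variance, no test statistic.

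The contrast may still differ between years through b4. The random country-by-year effect and the arm-specific R-matrices add no asthma-specific treatment effect.

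**Asthma model with the interactions.** Adding b5·T·A + b6·Y·A + b7·T·Y·A makes the difference b5 in the 1st year and b5 + b7 in the 2nd. Each has rank 1, so the 1-df test exists.

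**Tertile model as written.** With main effects only, all three contrasts equal the single treatment coefficient and the 2-df difference matrix has rank 0. With treatment x tertile it has rank 2.

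**Illustration (assumed values, one simulated data set of 440, single season, SD 5.5, 30% with asthma).** With true effects of -2.2 without asthma and -0.2 with asthma, the additive model returned -1.46 for both groups and the interaction model returned -1.95 and -0.12. This shows the mechanism and says nothing about the trial's likely result.

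**Precision of the corrected asthma test.** The inputs from SAP section 7 are SD 5.5, difference 1.64 and 180 evaluable per arm. They reproduce the plan's 80% power: SE = 5.5·√(2/180) = 0.58 and power = Φ(1.64/0.58 − 1.96) ≈ 0.81. The documents give no asthma share p, so take p from 0.2 to 0.5 as an assumption. For one season,

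SE(interaction) = 5.5·√(2/(180p) + 2/(180(1−p))).

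- p = 0.2: SE 1.45; power for an interaction of 1.64 = Φ(1.64/1.45 − 1.96) ≈ 20%.
- p = 0.5: SE 1.16; power = Φ(1.64/1.16 − 1.96) ≈ 29%.

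**Why the tertile test needs more than an interaction term.** SAP Appendix B lists 46 sites. For 440 subjects, 440/46 ≈ 9.6 per site, or about 4.8 on placebo, assuming equal site sizes. The sampling variance of a site's placebo mean is 5.5²/4.8 ≈ 6.3 (SE 2.5). Assume a true between-site SD of 0 to 2. The share of variation in the ranking variable that is real is then 0 to 4/(4 + 6.3) ≈ 39%. A site placed in the top third is there largely because its placebo subjects scored high by chance, and those same scores are then subtracted in its treatment contrast.

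Approximate size: the means of the top and bottom thirds of a normal variable lie 2 × 1.09 = 2.18 SDs apart. The noise part of the gap in placebo means is 2.18 × 6.3/√(SD² + 6.3).

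- Between-site SD 0: about 5.5 TCS points.
- Between-site SD 2: about 4.3 points.

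With 440/6 ≈ 73 subjects per arm and tertile, the SE of a difference between two tertile contrasts is about 5.5·√(4/73) ≈ 1.3. The spurious gap is thus roughly 3 to 4 SEs. This agrees with simulation (440 subjects, 46 sites, SD 5.5, between-site SD 0 to 2, no true interaction), in which the treatment x tertile test on TCS rejected at 5% in 87% to 99.8% of trials. The false signal points the way the section's hypothesis expects: a larger benefit where placebo scores are high.

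**The case against.** The strongest reply is that the intention is plain. Both sections ask for subgroup-specific contrasts and a test between them, and only a model with an interaction can deliver those, so this is an incomplete model line rather than a decision to omit the term. That is a fair reading and it limits the seriousness. It does not supply the term. The SAP writes out treatment x year in the same sentence, and the choice between a two-way and a three-way asthma interaction stays open.

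A reader might infer that the analyses would print one effect under each label and so pass as perfect consistency across subgroups. The documents do not support that. A 0-df comparison gives no p-value, so the gap would be visible. Under the square-root transformation in SAP 9.5.1, the back-transformed differences need not even look equal. With assumed root-scale means of 2.6 versus 2.3 without asthma and 2.9 versus 2.6 with asthma, the contrast is -0.3 in both, yet the back-transformed differences are 2.3² − 2.6² = -1.47 and 2.6² − 2.9² = -1.65. Such variation is an artefact of different subgroup means and not evidence of effect modification.

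The analyses are also outside the hierarchy in SAP 4.1, and even the corrected asthma test would be weak. Both points stand. They argue for cautious interpretation, not for leaving an uncomputable test in the plan.

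**Conclusion.** The models as written are wrong for their stated purpose. On the model scale the contrasts are identical across asthma levels within each year, and across tertiles. The planned tests have 0 df. This is algebra and rests on no assumption about the data.

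A reader might go further and infer that the trial's main conclusions are at risk. They are not: the primary and key secondary analyses do not need these terms.

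A reader might also infer that adding treatment x tertile repairs SAP 6.3.1.3 just as the asthma interactions repair 6.3.1.1. It does not. Tested on tertiles built from the same placebo TCS values, that term would usually be significant when no interaction exists. The 87% to 99.8% figure rests on an assumed between-site SD of 0 to 2 and an SD of 5.5, and was obtained for TCS only. RQLQ would be affected to the extent that it correlates with TCS. The 20% to 29% power figure rests on the assumed asthma share.

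**What to change.** **SAP 6.3.1.1.** Add treatment x asthma, year x asthma and treatment x year x asthma to the fixed effects. Output the treatment contrast per asthma level and year, and test their difference within each year (1 df), pooled over imputations by Rubin's rules. State that power is low and that a non-significant result is not evidence of equal effects. The imputation in SAP Tables 5 to 7 already samples within asthma status, which suits this model. SAP 9.5.2 allows asthma status to be dropped from the imputation; if that happens, say so beside the result, because it would dilute any interaction.

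**SAP 6.3.1.3.** Add treatment x subgroup so that tertile-specific contrasts exist, and choose one of two routes:

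- Group sites by a measure independent of the placebo outcomes, such as the station pollen counts already collected, and test the interaction per year (2 df). Several sites share a station, so the thirds will be uneven.
- Keep the placebo-based tertiles, show the contrasts descriptively with no interaction p-value, and note that selection on placebo means inflates the apparent gradient.

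The cost is SAP wording and two model statements, with no new data and no effect on subjects. If the SAP can no longer be amended before unblinding, document the change in the trial report, as protocol section 15 requires for departures from the final SAP. Which estimands the asthma analysis covers (SAP Table 4 against 6.3.1.1) is a separate question and should be raised separately.

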6.3.1.2 Subjects from the same household

The subjective nature of PRO measure may influence the overall quality of the data Chang et al. 2019. Multiple factors can impact the truthfulness of the data, but in this supportive analysis, the aim is to investigate whether subjects from the same household can influence each other's evaluation of symptoms.

This evaluation will be done by removing all subjects from the same households from the analysis. The list of subjects will be provided in the supplementary document to the SAP: Documentation of Trial Analysis Sets before DBL. The evaluation will be done on the primary endpoint (TCS during PGPS) and the first key secondary endpoint (RQLQ during PGPS). The analysis is done using primary estimands, the main analysis approach.

If there is no, or minimal influence, the results are expected to be similar to those using all subjects' data. This analysis will be done only if in total 10 subjects will be from the same household.

6.3.1.3 Symptoms-score tertiles analysis

Howarth *et al.* (2012) examined effects of allergen immunotherapy where study sites were grouped by the level of allergic rhinoconjunctivitis symptoms (low, medium, high) among placebo-treated subjects. The hypothesis was that sites where the symptoms scores were the highest under placebo, the seasonal disease activity was the highest and, presumably, therefore an effect of the allergen immunotherapy could potentially be greater here than at sites where the symptoms scores under placebo were lower.

To address this, trial sites will be grouped into tertiles according to the trial sites' placebo mean TCS in the PGPS based purely on observed TCS values (i.e. no imputation) for each of the two years (2022 and 2023), respectively. TCS and RQLQ will be analysed for the PGPS using the

Statistical analysis plan	Date:	27-Oct-2023	
Trial ID: SU-G-01	Version:	1.0	
EudraCT No.: 2020-000455-12	Status:	Final	
CONFIDENTIAL	Page:	29 of 47	

ALK

DPS1/on-treatment observation period data. The model(s) will be ANCOVAs run for each year separately. The model will include treatment, seasonal-disease-activity-subgroup and asthma strata as fixed effects and allowing unequal residual variances among the two treatment arms.

Treatment contrasts corresponding to each level of trial-site-subgroup will be output along with (multivariate) tests of (year-specific) subgroup effects: that is, for each year, whether the three treatment contrasts (corresponding to the three tertiles subgroups) are statistically significant from one another.

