4.1 Multiplicity adjustment

The trial product estimand is the primary estimand for all endpoints. The analyses for the primary and for the three key secondary endpoints will be controlled for multiplicity to ensure a family wise type I error rate is no larger than 5%.

The multiplicity will be controlled by employing a hierarchical testing procedure by prespecifying the order of the hypothesis to be tested. For the primary and key secondary endpoints the null hypothesis tested, is the hypothesis no difference between placebo and 5grass mix SLIT-drops treatment group.

The testing order of hypothesis is:

- 1. The primary efficacy analysis of the average daily allergic rhinoconjunctivitis TCS during the 2nd PGPS.
- 2. The key secondary efficacy analysis of average weekly overall RQLQ score during the 2nd PGPS.

Statistical analysis plan	Date:	27-Oct-2023	
Trial ID: SU-G-01	Version:	1.0	
EudraCT No.: 2020-000455-12	Status:	Final	
CONFIDENTIAL	Page:	16 of 47	

- 3. The key secondary efficacy analysis of average daily allergic rhinoconjunctivitis TCS during the 1st PGPS.
- 4. The key secondary efficacy analysis of average weekly overall RQLQ score during the 1st PGPS.

The primary endpoint is the 1st hypothesis in the hierarchy and will be tested on a 5% significance level. The testing of endpoints from the 2nd to the 4th in the hypothesis hierarchy will only be is only carried out formally if all previously tested hypotheses are statistically significant at the 5% level.

Additional endpoints and analyses are supportive in nature, thus they will not be controlled for multiplicity.

5 Analysis sets

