6.1.1 Considerations regarding countries

Variation between different countries and sites are expected due to variation in geography and climate and thus grass exposure which may affect assessments. Further, variation in standard treatment procedures, and possible differences in the conduct of the trial are expected to vary between countries. Variation between sites (centres) is also expected but is assumed to be small compared to the variation between countries. The major source of variability is expected to be pollen exposure. Some sites can have very few subjects making it unreasonable to include sites as a covariate in the analysis model. In this trial, country is used as a covariate in the models.

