8.5 Pollen counts

Pollen season definitions are provided in Section 9.1. Pollen counts will be summarised by treatment group and total. Pollen counts will be weighted by the number of subjects in each pollen station and divided by the number of subjects in the trial. In addition, lengths of EGPS and for each year will be summarised. Lengths of EGPS will also be weighted as pollen counts.

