9.1 Definition of pollen seasons

Each trial site was allocated to a pollen station. The start and stop dates of the grass pollen seasons will be based on the daily pollen counts as defined in Table 10. The pollen EGPS dates will be within a period of expected pollen season defined trial protocol (see Trial Protocol, Appendix 5: Expected grass pollen season).

Start date of EGPS	The first day of 3 consecutive days with (non-missing) pollen count larger than or equal to 10 grains/m ³ .
Stop date of EGPS	The last day of the last occurrence of 3 consecutive days with (non-missing) pollen count lager or equal to 10 grains/m ^{3.}
PGPS	The 14 consecutive days period with the highest average pollen count during the entire grass pollen season.

Table 10 Grass pollen season definitions.

Based on the definition above, if the EGPS is shorter than 14 days, than PGPS will be equal to EGPS. In addition, a visual inspection of the pollen count (pollen grains/m3 versus time) will be made to validate the pollen counts in the season.

In case of missing pollen counts for specific pollen regions the 3 following principals will be used prior to unblinding:

• If pollen counts for maximum 2 days will be missing with at least 5 days with observed pollen counts days then the missing pollen counts (after first occurrence of pollen) will be replaced by applying the last observation carried forward method.

- If pollen counts will be completely missing or missing for extended period of time for a specific pollen station then a replacement pollen station will be manually assigned.
- In all other cases of missing pollen counts start and stop dates will be defined by visual inspection of the pollen counts for the specific pollen station and neighbouring pollen stations to approximate the general approach specified above.

Pollen seasons (i.e., actual start and end dates or start and end dates based on visual inspection) will be defined prior to database lock and further specified in Appendix B: pollen seasons start and stop dates.

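### Sorting sites into tertiles by placebo TCS, then comparing active with those same placebo subjects, creates a larger effect at high-symptom sites even when there is none

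*SAP*

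**What the plan says.** SAP 6.3.1.3 follows a published approach that groups sites by symptom level under placebo. Its premise is that at "sites where the symptoms scores were the highest under placebo, the seasonal disease activity was the highest", so that immunotherapy might show a larger effect there. Sites are split into tertiles by "placebo mean TCS in the PGPS based purely on observed TCS values (i.e. no imputation"), once per year. TCS and RQLQ in the same year's PGPS are then analysed on observed on-treatment data with one ANCOVA per year: "The model will include treatment, seasonal-disease-activity-subgroup and asthma strata as fixed effects", with residual variances allowed to differ by arm. The outputs are a treatment contrast in each tertile and a test, per year, of whether the three contrasts differ. The section has no leave-one-out step, no external grouping measure and no caveat.

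Elsewhere the SAP says of variation in assessments (6.1.1): "The major source of variability is expected to be pollen exposure". It also links sites to daily pollen data (9.1): "Each trial site was allocated to a pollen station". Section 8.5 already plans a summary of those data: "Pollen counts will be weighted by the number of subjects in each pollen station". The tertile analysis lies outside the testing hierarchy (4.1): "Additional endpoints and analyses are supportive in nature, thus they will not be controlled for multiplicity".

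**The concern.** The placebo outcome is used twice, as the sorting variable and as the comparator. Sites whose few placebo subjects happened to score high move into the top tertile, and sites whose placebo subjects happened to score low move into the bottom one. The active subjects are not selected in this way. The top-tertile contrast is therefore pushed toward benefit and the bottom-tertile contrast toward harm, which is the pattern the section sets out to look for. A reader shown a larger effect in the top tertile, with a small p-value for the difference, could conclude that the product works better where disease activity is high, although the grouping rule produces that result by itself. RQLQ is affected too, to the extent that it correlates with TCS.

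**Working it through.** **Inputs from the documents.** Evaluable subjects per arm 180, common TCS SD 5.5, assumed effect 1.64 (SAP section 7). Randomised 445, 1:1 (SAP 3.2). The only randomisation stratum named is asthma (SAP 3.2.3), so placebo numbers per site are not fixed. Appendix B, counted by hand, lists 46 sites on 21 pollen stations.

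**Assumptions.** The documents give no between-site SD, site sizes or TCS-RQLQ correlation. I varied the between-site SD from 0 to 4 with the total SD held at 5.5.

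**The plan's own figure.** Power at 180 per arm: SE = 5.5 × √(2/180) = 0.58; 1.64/0.58 = 2.83; Φ(2.83 − 1.96) ≈ 0.81. The stated 80% reproduces. The tertile analysis has no stated figure.

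**Noise in the sorting variable.** 180/46 = 3.9 placebo subjects per site (222/46 = 4.8 if all randomised count). The SE of a site's placebo mean is 5.5/√3.9 = 2.8 points, larger than the assumed effect of 1.64.

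**Bias by formula.** Let s_b² be the between-site variance, s_w² = 5.5² − s_b², and n = 180/46. The bias in the top tertile's placebo mean is

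E[Z | top third] × (s_w²/n) / √(s_b² + s_w²/n), with E[Z | top third] = 1.09.

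At s_b = 3: s_w²/n = 21.25/3.91 = 5.43, and 1.09 × 5.43/√(9 + 5.43) = 1.56. The bottom tertile has the same bias with the opposite sign.

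**Simulation.** 360 evaluable subjects, 46 sites, equal or varied sites, 1:1 allocation not stratified by site, normal scores, 1,500 to 2,000 runs per setting. The treatment-by-tertile term implied by the plan was added, with arm-specific residual variances. Contrasts are placebo minus active, with a true effect of 0 at every site.

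| Between-site SD (share of variance) | Top-tertile bias, formula | Simulated low / middle / high | Rejection by nominal 5% test |
|---|---|---|---|
| 0 (0%) | 3.03 | -2.9 / 0 / +2.9 | 96-99% |
| 2 (13%) | 2.24 | -2.1 / 0 / +2.0 | 76-87% |
| 3 (30%) | 1.56 | -1.5 / 0 / +1.5 | 52-66% |
| 4 (53%) | 0.90 | -0.9 / 0 / +0.9 | 27-38% |

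The high tertile exceeded the low one in at least 93% of runs in every setting; 50% is expected without bias.

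**Variations.**
- True effect 1.64 at every site: -1.3 / 1.6 / 4.5 at SD 0, and 0.2 / 1.6 / 3.1 at SD 3.
- Arm SDs 6.50 and 5.09 (SAP Table 8, P05238): rejection 99%, 92%, 79% and 56% at SD 0, 2, 3 and 4.
- Square-root scale: about 95%, 74%, 53% and 28%.
- RQLQ, assuming a correlation with TCS of 0.5-0.7: 34-65% at SD 0, 15-24% at SD 3, 9-13% at SD 4.

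**Same analysis, grouping independent of outcomes.** With a station-level measure on the actual 21-station map, contrasts lie within 0.1 of the truth and the test rejects in 4-6% of runs, with equal or Table 8 SDs.

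**Pooling both arms.** Grouping by the site mean over both arms gives unbiased contrasts when the SDs are equal, with rejection of about 5% (7-9% when the two arms' site averages are weighted equally). With 6.50/5.09 it rejects in 16%, 11% and 10% of runs at SD 0, 2 and 3. With 5.48/4.06 (GT-08 2006) it rejects in 23%, 13% and 12%. The bias runs in the same direction.

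**The case against.** The analysis is supplementary and not multiplicity-controlled, its hypothesis is worded tentatively, and SAP 3.1.1 does not list it among the planned supplementary analyses. It follows a published grouping and was specified before unblinding. The row with no site differences is also the least plausible. The SAP expects pollen exposure to dominate, and the listed ANCOVA has no country term, so country differences count as between-site spread. On that reading the SD 4 row is nearer the mark.

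The limited reach stands, and it sets the importance of the point. The remark about plausible spread is fair and applies to the size. It does not rescue the test, which at SD 4 still rejects at more than five times its nominal rate. Precedent and prespecification do not remove a bias built into the grouping rule.

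Two objections to the remedy also have force. Pollen tertiles measure exposure and not symptoms under placebo, and correct rejection rates do not show that they separate disease activity well. The case against pooling both arms depends on unequal SDs; under the plan's common SD it is much less of a problem.

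**Conclusion.** The concern holds. Followed exactly, SAP 6.3.1.3 gives biased tertile contrasts and an invalid test of their equality. With no true effect, the top and bottom tertiles are each off by about 0.9 to 2.9 TCS points, in opposite directions, and the 5% test rejects in roughly 27% to 99% of trials as the between-site SD falls from 4 to 0. The size rests on the assumed between-site SD and site sizes and, for RQLQ, on its assumed correlation with TCS. The direction follows from the rule itself and held in every setting. The harm is confined to this supplementary analysis; the primary and key secondary tests are untouched. The section should be corrected, but the trial's main conclusion does not depend on it.

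A secondary point of wording: the listed terms contain no treatment-by-subgroup interaction, so the treatment contrast would be identical at every level. The promised contrasts imply that the term is intended. The asthma subgroup model in 6.3.1.1 has the same gap, listing "treatment, year; treatment and year interaction, and ongoing asthma status as fixed effects".

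**What to change.** Define the tertiles for each year from a measure that does not use subject outcomes, such as the mean PGPS pollen count at each site's station, and fix them before unblinding. Add treatment × tertile to the ANCOVA. This also places any site that has no observed placebo subject, which the current rule cannot.

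If comparability with the published work matters more, keep the placebo-mean grouping as a descriptive display, state the bias and its direction beside it, and drop the test of difference. I would not substitute the site mean pooled over both arms, given the unequal SDs in Table 8.

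For clarity in 6.3.1.1, list treatment × ongoing asthma and treatment × ongoing asthma × year.

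The cost is SAP wording and model statements, on data already held. The pollen grouping has drawbacks that should be stated: only 21 stations for 46 sites, with single stations serving 7, 6 and 6 of them; two Czech stations relying on a third station's data in 2023; partial overlap with country; and loss of the match with the cited method.
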